Primary objective: To determine if combined treatment with dapagliflozin and metformin is more effective than monotherapy with metformin for weight loss and assess its effects on waist circumference, triglycerides, blood pressure and inflammatory cytokines (resistin, adiponectin, interleukin-6 and interleukin-10) in prediabetic and diabetic patients with obesity class III.

Secondary objective: To determine the effect of combined treatment with dapagliflozin and metformin in comparison with monotherapy with metformin on serum concentrations of glucagon, ghrelin and insulin.

Patients, material and methods: The protocol includes patients with previous or recently diagnosed diabetes or prediabetes from the Obesity Clinic of CMN SXXI from July 2018 to August 2023 age 18 to 60 years old, both male or female and not treated with insulin. Patients requiring initial treatment with insulin, with obesity secondary to other comorbidities and patients who do not wish to enter the study or not provide their informed consent will be excluded. Patient's data that during the study are advised to undergo bariatric surgery will be used until the moment of surgery. Other treatments will be adequately recorded. Patients will be randomized by computer software and assigned in a group treated with metformin (>2 g/day, group 1) or with metformin (>2 g/day) and dapagliflozin 10 mg (group 2). All patients will receive dietary treatment and follow-up by the Nutrition service during the study. Anthropometric and biochemical variables will be recorded at the beginning and at months 3, 6 and 12. Adherence to treatment will be assessed, defined by consumption of at least 90% of provided pills. The adverse events will be recorded since the beginning of study and will be ranked according to the CTCAE lists (Common terminology criteria for adverse events version 4.03). An intention-to-treat analysis will be performed in case of patients that require treatment with insulin.

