6. OBJECTIVES

- a. **Primary objective:** To determine if combined treatment with dapagliflozin and metformin is more effective than monotherapy with metformin for weight loss and assess its effects on waist circumference, triglycerides, blood pressure and inflammatory cytokines in patients with prediabetes and diabetes with obesity class III.
- b. **Secondary objectives:**
 - i. To determine efficacy of metformin monotherapy for weight loss and decrease on waist circumference, triglycerides and blood pressure in patients with prediabetes and diabetes with obesity class III.
 - ii. To compare efficacy of metformin monotherapy and combined treatment with metformin and dapagliflozin.
 - iii. To determine the percentage of patients that with combined treatment achieves a decrease in total weight of 5%, 10% and 15% and the percentage of patients that achieve a decrease in 10% of excess weight.
 - iv. To evaluate if combined treatment allows a decrease in number of drugs needed for comorbidities' control.
 - v. To evaluate prevalence of adverse effects commonly associated with dapagliflozin use (urinary and genital tract infections, hydroelectrolytic alterations) in patients with obesity class III.
 - vi. To determine serum concentration of adiponectin, resistin, IL-6, IL-10 and TNF- α before and after treatments, and compare it between groups.
 - viii. To determine serum concentration of insulin, glucagon and ghrelin before and after treatments, and compare it between groups.

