Santo et al. in 2014 conducted a prospective study for evaluating possible benefits related to pre-surgical weight decrease in patients with super-obesity. In this study, 20 patients had in-hospital strict dietary control with diets between 600 and 1500 kcal plus aerobic physical activity (in those allowed to do it). Patients obtained a reduction of 19.7% of initial weight, with decrease of BMI

from 67 kg/m² to 55 kg/m² over a 24-weeks period. In this group, they observed a lower incidence of complications and decreased time of hospitalization [11].

Prevalence of comorbidities in the Obesity Clinic

The Obesity Clinic evaluates a population of approximately 400 patients, 150 patients have undergone bariatric surgery, 250 patients are pending of approval for such proceedings and up to 10 new patients per month are assessed for determine its possible admission to the clinic.

Sanchez-Ruiz et al. previously performed a retrospective study with a sample of 109 patients from the Obesity Clinic who underwent bariatric surgery between January 2009 and December 2011 (in press). In this study, the mean age was 45.3 ± 10.1 years, 70% were female, 85% reported attachment to diet (up to 80%), 31% performed physical activity (defined as at least 30 minutes of daily walking), 21% were smokers, 74% had a family history of obesity and 67% reported overweight or obesity since childhood. In this study, we observed that 46% of patients had prediabetes (defined by the American Diabetes Association, [ADA] as a plasmatic fasting level greater than 100 mg/dl and less than 126 mg/dl or a 2-h plasma glucose level measured after a 75-g oral glucose load, greater than 140 mg/dl and less than 200 mg/dl) or T2D (defined as fasting glucose greater than 126 mg/dl or a glucose level post-load greater than 200 mg/dl) [12], 66% had HTN and 33% had dyslipidemia (hypertriglyceridemia, hypoalphalipoproteinemia, or both). At this clinic, patients with prediabetes or T2D are usually treated with metformin 2 g/day or Neutral Protamine Hagedorn insulin (NPH) with calculated doses of 0.5 to 1 U/kg of weight when necessary and are evaluated every three months for treatment adjustment depending on their glycated hemoglobin as stipulated by ADA guidelines [12].

Pharmacological treatment of obesity

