8. PATIENTS, MATERIAL AND METHODS

Type of study: Phase II/III, controlled, randomized, open clinical trial.

By study groups: two parallel groups' design.

By maneuvering: experimental

By measurements in the population: longitudinal

By temporality: prospective

By the nature of the study: clinical

By purpose: Therapeutic

Study Population

- Patients with obesity class III from the "Obesity Clinic" in preparation for bariatric surgery.
- Study period: December 2016 to October 2018
- Place of study: Mexico City, Mexico
- Time of clinical assessment of each patient: one year

Workplan

- 1) A convenience sampling will be done for patients diagnosed with diabetes or prediabetes according to ADA criteria [12] (Appendix 1), who come to Obesity Clinic in the indicated period and that meet the selection criteria. Since the first assessment, patients are informed that they would become candidate for bariatric surgery (bypass or gastric sleeve, depending on surgeons' criteria) once they achieve a weight reduction of 10%.
- 2) Due patients achieve weight loss needed for the surgical procedure at different times of follow-up (3, 6 or 12 months), clinical, biochemical, and initial and final determinations of inflammatory cytokines and hormones, will be collected until the previous valuation before surgery. Data will be collected even if the patients require treatment with sulfonylureas or insulin (adverse event grade 3).
- 3) Prevalence of comorbidities at baseline and the type and dose of drugs used for treatment will be recorded (Appendix 2. Data Collection Sheet). Treating physicians based on the clinical response of patients, will decide the dose and number of drugs and will record changes in the corresponding data sheet.

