- 8) The determination of blood pressure will be performed by a nurse from the Obesity Clinic, using an aneroid sphygmomanometer, recording the average of two measurements taken with a 5-minutes difference, according to the procedure's manual for the assessment of clinical and anthropometrical measurements in the adult and elderly of the Ministry of Health (Appendix 3. takes clinical and anthropometric measurements).
- 9) The determination of insulin, glucagon, ghrelin, adiponectin, resistin, IL-6, IL-10 and TNF- α will be held at baseline and before surgery (depending on the response of each patient). For the determination of these cytokines and peptides, an ELISA kit (enzyme linked immunosorbent assay) will be used (Appendix 4. ELISA technique).
- 10) Adherence to treatment will be evaluated and will consist in consumption of 90% of pills granted. The registration of adverse events will take place from the start of treatment and throughout the study. Each event will be evaluated by researchers and classified according to CTCAE list (Common terminology criteria for adverse events version 4.03). CTCAE considers that an adverse event grade 4 or 5 indicates discontinuation of treatment; grade 3 must be submitted to review by the medical team, and grades 1 or 2 require registration and intervention but not discontinuation of treatment (Appendix 5. CTCAE list). Adverse events will be recorded in the report sheet (Appendix 6. Sheet report for drug side effects).
- 11) The patients that do not achieve weight loss at one-year follow-up will be discarded to their primary care hospital as pre-specified by the Obesity Clinic internal regulation.

Selection criteria

Inclusion criteria

- 1. Age from 18 to 60 years
- 2. Any gender
- 3. BMI greater than or equal to 40 kg/m²
- 4. Diagnosis of diabetes or prediabetes according to the criteria of the ADA. Patients must have glycated hemoglobin less than 9%.
- 5. Patients who sign informed consent letter (Appendix 7. Charter informed consent)
- 6. Candidates to bariatric surgery

Exclusion criteria

- 1. Current use of insulin or sulfonylureas
- 2. Chronic kidney disease with glomerular filtration rate <60 ml/min/1.73 m²
- 3. Use of loop diuretics with no possibility to suspend.

4. Concomitant illnesses that predispose to volume depletion, weight loss (including oncological diseases), or metabolic acidosis (including drug users)
5. History of recurrent genital or urinary tract infections

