Age	Quantitative, continuous	Ratio	Time elapsed from birth to	Time elapsed from birth to the baseline registry of the patient.	years
-----	--------------------------	-------	----------------------------	--	-------

			the current date.		
Gender	Qualitative, dichotomic	Nominal	Taxon that gathers members of the same species.	Gender assigned in the registry documents.	0 = female 1 = male
Height	Quantitative, continuous	Ratio	Length of a human body when measured in a standing position from the top of head to the floor.	Height registered in the baseline documents using the same stadiometer in all patients during the first evaluation.	meters (m)
Body mass index (BMI)	Quantitative continuous	Ratio	Measurement that associates height and size in the same individual and classifies them as underweight, normal, overweight or obese.	Ratio between weight in kilograms (kg) divided by the square of the height in meters. Calculation is performed in every clinical evaluation during the protocol.	kg/m²
DEPENDENT VARIABLES					
Weight	Quantitative continuous	Ratio	The force that gravitation exerts upon a body.	Total amount of kilograms registered in the same person using the same calibrated scale at baseline and months 3, 6 and 12.	kilograms (kg)

Waist circumference (WC)	Quantitative continuous	Ratio	Measurement of the body circumference measured at the minimum circumference between the iliac crest and the rib cage.	Perimeter registered in the documents using the same flexible tape at baseline and months 3, 6 and 12.	centimeters (cm)
Fasting Glucose	Quantitative continuous	Ratio	Glucose concentration in the blood serum after an 8 hour fast.	Blood glucose reported at baseline, months 3,6 and 12.	mg/dl
Fasting Insulin	Quantitative continuous	Ratio	Insulin concentration in the patients serum determined by radioimmunoassay after an 8 hour fast.	Blood insulin reported at baseline and months 3,6 and 12.	mU/L
HOMA-IR	Quantitative continuous	Ratio	The homeostatic model assessment (HOMA) is a method used to quantify insulin resistance and beta-	HOMA = [glucose (mg/dl)/18 *insulin (mU/L)]/22.5 at baseline and months 3,6 and 12.	Dimensionless

			cell function.		

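### The plan has no rule for serum insulin and HOMA-IR values drawn after a patient starts injected insulin

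*Combined protocol and SAP*

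**What the plan says.** Current insulin use is an exclusion criterion, so baseline insulin is the patient's own. After entry, Workplan item 2 in Section 8 keeps collecting: "Data will be collected even if the patients require treatment with sulfonylureas or insulin (adverse event grade 3"). The Abstract adds: "An intention-to-treat analysis will be performed in case of patients that require treatment with insulin". Starting insulin is not among the withdrawal criteria.

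Serum insulin is compared between arms under secondary objective viii: "To determine serum concentration of insulin, glucagon and ghrelin before and after treatments, and compare it between groups". HOMA-IR is listed as a dependent variable in Section 8: "HOMA = [glucose (mg/dl)/18 *insulin (mU/L)]/22.5 at baseline and months 3,6 and 12". The Statistical analysis paragraph gives a REML mixed model with assigned treatment, sex and glycaemic status as fixed effects. It has no term for insulin use and no rule for these two variables once insulin has started. C-peptide is not measured.

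The plan gives two accounts of how and when insulin is measured. The variable table has "Insulin concentration in the patients serum determined by radioimmunoassay after an 8 hour fast", with "Blood insulin reported at baseline and months 3,6 and 12". Workplan item 9 names ELISA, and says the determinations "will be held at baseline and before surgery (depending on the response of each patient"); item 2 likewise speaks of initial and final hormone values. Section 7 describes the clinic's usual insulin as "Neutral Protamine Hagedorn insulin (NPH) with calculated doses of 0.5 to 1 U/kg of weight when necessary".

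**The concern.** Keeping patients after insulin starts is sound for weight, where the outcome stays a valid measurement whatever else the patient takes. Serum insulin is different: the added drug is the analyte. An assay that does not separate injected from endogenous insulin returns their sum, and HOMA-IR is proportional to that sum.

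One arm receives an extra glucose-lowering drug, which the Abstract credits with reducing HbA1c by 0.4 to 0.8%. The trial is open, and treating physicians decide other drugs. More frequent insulin use on metformin alone is therefore a reasonable expectation. The artefact would be lower measured insulin on the combination. Section 7 already reports lower insulin with dapagliflozin, in rats and in a small patient series, so a reader could not tell artefact from effect.

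**Working it through.** **Inputs.** The documents give no rate of starting insulin, no mean or SD for insulin, and no assay specificity. The following are assumptions: fasting insulin has mean 20 and SD 10 mU/L, injected insulin adds 10, 20 or 40 mU/L to the reading, and there is no true difference between arms. The 45 per arm comes from the sample-size section. It reproduces as 2 × (1.96 + 0.84)² × 4.22² / 2.5² ≈ 45, but it was set for weight and serves here only as an illustrative size.

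**Serum insulin.** Let pM and pD be the shares on injected insulin at sampling in the metformin and combination arms.

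Bias (metformin minus combination) = (pM − pD) × added reading.

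For example, (0.20 − 0.05) × 20 = 3.0 mU/L. The false-positive rates come from 20,000 simulated trials per cell, each analysed with a two-sided Welch test at 0.05. That is a simpler test than the planned mixed model.

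| On insulin, metformin / combination | Adds 10 mU/L | Adds 20 mU/L | Adds 40 mU/L |
|---|---|---|---|
| Equal (5/5, 10/10, 20/20%) | 0; about 5% | 0; about 5% | 0; about 5% |
| 10% / 5% | 0.5; 5.3% | 1.0; 6.8% | 2.0; 9.3% |
| 20% / 10% | 1.0; 7.3% | 2.0; 12.1% | 4.0; 18.9% |
| 20% / 5% | 1.5; 10.1% | 3.0; 21.7% | 6.0; 39.8% |
| 30% / 10% | 2.0; 14.3% | 4.0; 31.8% | 8.0; 52.7% |

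Each cell shows bias in mU/L, then the false-positive rate. An excess of 5 percentage points in 45 patients is 0.05 × 45 = 2.25, or about two patients.

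**HOMA-IR.** By the plan's formula, with assumed values for one patient:

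- Glucose 110 mg/dl, insulin 20 mU/L: (110/18 × 20)/22.5 = 5.4.
- Glucose 110, insulin 40: 10.9. The index doubles with no change in resistance, but only because glucose was held fixed.
- Glucose 250, insulin 20 (before insulin is started): (250/18 × 20)/22.5 = 12.3.
- From 250 and 20 to 110 and 50: 12.3 to 13.6, a rise of about 10%.
- From 250 and 20 to 110 and 40: 12.3 to 10.9, a fall of about 12%.

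The index is uninterpretable after insulin starts, yet its net movement can go either way.

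**Which follow-up values exist.** Under the variable table, a patient who starts insulin after month 3 has a clean month 3 value. Under Workplan items 2 and 9, the same patient has only a baseline value and a final value, and the final value is the contaminated one.

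**The case against.** The strongest reply is that intention to treat is the right principle, that the variable definition literally covers all insulin in serum, and that few patients may be affected. Entry requires HbA1c below 9%, admits prediabetes and excludes insulin users. Drug changes are recorded, so a later sensitivity analysis is possible in any case.

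Much of this stands. Insulin use may be rare, and the size is unknown. Assay detection is an assumption: the method is unsettled, NPH is described only as usual clinic care, the Abstract says only basal insulin, and no product is named for the trial.

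A reader might infer that the retention rule alone biases both outcomes by arm. The documents do not support that: unequal use is also needed, and no rates are given. A reader might also infer that HOMA-IR would be inflated on metformin alone. That does not follow, because glucose falls when insulin is given. Nor does the point extend to sulfonylureas, which the same sentence of the plan covers. They raise the patient's own insulin, so the assay still measures what it should.

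Intention to treat settles which patients are analysed. It does not make a reading of injected drug a measure of insulin resistance, which is what the variable table says HOMA-IR quantifies. Excluding the values has its own weakness: the gaps fall on patients with poor glycaemic response and may be unequal by arm.

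**Conclusion.** The gap is real and follows from the plan's text. As written, values that may contain injected insulin enter the arm comparison of serum insulin and the calculation of HOMA-IR. Three conditions govern the consequence. The assay must detect the injected product. For arm bias in serum insulin, use must be unequal; if it is commoner on metformin alone, the bias favours the combination. The size then depends on rates and readings that the documents do not give: zero at equal use, small if use is rare, and several mU/L with a false-positive rate well above 5% if use is common and unequal. For HOMA-IR, only loss of meaning is established, not size or net direction.

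The stakes are secondary. Insulin is a secondary objective, HOMA-IR appears only in the variable table, and the weight comparison is not touched by this problem. The change is still worth making in advance, because it is cheap and the artefact would look like a drug effect.

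**What to change.** First reconcile the insulin schedule and assay: initial and final by ELISA in Workplan items 2 and 9, against months 3, 6 and 12 by radioimmunoassay in the variable table. This decides whether any pre-insulin follow-up value exists.

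Then add a short rule to the Statistical analysis paragraph:

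- Patients who start injected insulin stay in, with all other outcomes analysed as planned.
- For serum insulin and HOMA-IR only, values drawn after the first injected dose are treated as missing in the main analysis. The REML mixed model uses whatever pre-insulin values exist, without last-value substitution and without a new blood draw. Substitution would freeze values at the point of treatment change, selectively by response.
- The number of such patients is reported per arm.
- The analysis with all values is shown as a sensitivity analysis.

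The cost is a few sentences and a few lost values. The recorded drug changes identify the values affected. Because starting insulin reflects poor glycaemic response, the missingness is informative, and the report should say so. Under the initial-and-final schedule these patients contribute only a baseline value, which the model cannot repair.

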2. ABSTRACT

Introduction: According to the World Health Organization (WHO), obesity is an abnormal or excessive accumulation of fat, which could affect human health. Mexico has one of the highest prevalence of obesity, reported by 32.4% of people over 20 years old, according to National Health and Nutrition Examination Survey (ENSANUT, Encuesta Nacional de Salud y Nutrición 2012). This implies that 22 millions of Mexicans have obesity. Additionally, the prevalence of obesity class III (defined as a body mass index greater than 40 kg/m^2) is 1.8% (IC95% 1.5-2.1%) in males and 4.1% (3.7%-4.5%) in females.

The Mexican Social Security Institute (IMSS, Instituto Mexicano del Seguro Social) (that has one of the widest health coverages in the country) has reported a prevalence of obesity on its affiliates up to 74.4%, but only 50% had received clinical care for weight control (for example, diet or physical activity recommendations). In a recent article published by Barrera-Cruz et al. it is estimated that this disease reduces life expectancy from 6 to 20 years, being responsible for 2.8 million deaths per year in our country. In addition, it is estimated that it generates an annual cost of 3,500 million dollars for direct and indirect costs.

Since 2008, a multidisciplinary clinic focused on obesity treatment and related comorbidities has been organized at the Hospital de Especialidades of Centro Médico Nacional Siglo XXI. Currently, the "Obesity Clinic" attends a 400-patient population, of which 150 patients have undergone bariatric surgery (gastric bypass or gastric sleeve) and 250 patients are on waiting list and preparation for this procedure. According to previous data (not yet published) the mean age of these patients is 41 ± 9 years, 46% have pre-diabetes or type 2 diabetes mellitus, 66% has hypertension and 33% has dyslipidemia (hypertriglyceridemia, hypoalphalipoproteinemia or both). The management of glucose alterations on this unit is done with personalized diets supervised by the Nutrition Service of the Obesity Clinic and with the use of metformin at doses greater than 2 g/day and/or basal insulin at doses of 0.5 to 1 U/kg of patient's weight.

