5. HYPOTHESIS

Dapagliflozin in combination with metformin induce 10% of weight lost and 5% of decrease in waist circumference, triacylglycerol concentration, blood pressure and inflammatory cytokines in patients with prediabetes or diabetes with class III obesity, in comparison with the 5% of weight lost and lack of effect in the rest of parameters in patients treated with metformin monotherapy.

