The Mexican Social Security Institute (IMSS) has the broader coverage of health of the country. According to ENSANUT 2012, 74.4% of its beneficiaries are obese and it is estimated that only 50% receive medical attention focused on weight control (e.g. diet or physical activity recommendations). Considering the current increase in the prevalence of obesity and an imperious need of reducing the prevalence of co-morbidities and high mortality rate associated with this disease, since 2008 the Hospital de Especialidades from the Centro Medico Nacional Siglo XXI organized a multidisciplinary team composed by members from departments of Endocrinology, Clinical Nutrition, Bariatric Surgery, Psychiatry and Internal Medicine, under the name of "Obesity Clinic".

The requirements for admission are a BMI greater than 35 kg/m² with a major comorbidity (diabetes, hypertension, dyslipidemia or sleep apnea syndrome) or obesity class III. Patients are initially evaluated by nutritionists authorized to assess anthropometric measures, who also adjust diet based on weight and initial consumption of calories and evaluate patients monthly recording weight, waist and hip circumference, percentage of adherence to diet and amount of physical exercise per week (measured in minutes per week). At the same time, the endocrinologists perform clinical assessment and laboratory tests for detection and control of comorbidities such as altered metabolism of glucose (Type 2 diabetes [T2D] or pre-diabetes), hypertension (HTN) and dyslipidemia and request assessment and treatment of other specialists if necessary. Meanwhile, psychiatrists perform tests for detection and treatment of anxiety disorders or depression, eating disorders, personality disorders and other psychiatric comorbidities that could influence negatively on the management of patients and finally, once the patients lost 10% of excess of weight, they become candidates for bariatric surgery (laparoscopic Roux-Y bypass or gastric sleeve, depending on the evaluation of surgeons).

Several studies support that weight reduction before surgery decreases surgical risk and improves time to recovery. It has been observed that patients with super-obesity have a higher incidence of complications during bariatric surgery associated with increased technical difficulties (for example an increased liver volume due to steatosis), increased anesthetic risk and risk of treatment failure.

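### Workplan item 9 ties the only post-baseline sample of seven markers to surgery and states no final sample for patients who never have surgery

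*Combined protocol and SAP*

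**What the plan says.** All references are to the combined protocol and SAP.

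- **Sampling rule.** Section 8, Workplan item 9, names eight markers and says that their determination "will be held at baseline and before surgery (depending on the response of each patient". Item 2 says that "patients achieve weight loss needed for the surgical procedure at different times of follow-up (3, 6 or 12 months" and that "initial and final determinations of inflammatory cytokines and hormones, will be collected until the previous valuation before surgery".
- **Surgical target.** Workplan item 1 makes patients candidates "once they achieve a weight reduction of 10"%. The account of the Obesity Clinic in section 7 says "once the patients lost 10% of excess of weight, they become candidates for bariatric surgery".
- **Objectives.** Cytokines are in the primary objective. Secondary objectives vi and viii cover all eight markers; viii reads "To determine serum concentration of insulin, glucagon and ghrelin before and after treatments, and compare it between groups". Neither gives a month or restricts the comparison to surgical patients.
- **Expected difference.** Section 5 expects a 10% weight loss on the combination "in comparison with the 5% of weight lost and lack of effect in the rest of parameters" on metformin alone.
- **Variable table.** Adiponectin, resistin, IL-6, IL-10, ghrelin and glucagon have an assay but no time point. TNF-alpha has no row. Fasting insulin is the exception: it is scheduled at baseline and months 3, 6 and 12, by radioimmunoassay, whereas item 9 uses ELISA.
- **Data sheet (Appendix 2).** Initial and Final columns exist for six markers, without a month. The grid of months 1, 3, 6 and 12 omits them.
- **Patients without surgery.** Item 4 removes patients with poor diet adherence from the surgical protocol. Item 11 returns patients without weight loss at one year to their primary care hospital. Neither mentions a final marker sample.

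**The concern.** The time of the final sample, and on a literal reading whether it is taken at all, depends on weight loss. Weight loss is the outcome on which the trial is sized, and it is expected to differ between arms. Two things could go wrong.

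1. **Availability.** If only patients who reach surgery give a final sample, the marker comparison is made among responders. Randomisation no longer protects it, and few metformin patients would contribute.
2. **Timing.** If everyone is sampled, but responders earlier, the arms are compared at different durations of treatment.

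The mixed model in the Statistical analysis paragraph is meant for follow-up of unequal length. That suits weight, which is measured at several visits. It is weaker support for a marker with one post-baseline value taken at a month that is itself a result of response.

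**Working it through.** The plan gives no figure for marker sampling, so there is none to reproduce. The calculation below only sizes the two readings.

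**Inputs from the documents:** mean losses of 10% and 5% (section 5); 54 patients per arm (Sample size); visits at months 3, 6 and 12; a target of 10% of weight (item 1).

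**Assumptions:** month-12 loss is normal with SD 5 points (range 4 to 8), because the documents give no SD for percentage loss. Shares of that loss reached by months 3/6/12 are 25/50/100, 29/64/100, 43/80/100 and 50/80/100. The middle two take their shape from the metformin case series in section 7, a retrospective series of 30 non-diabetic women.

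**A. Literal reading: a final sample only if the target is reached**

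| SD | Combination | Metformin |
|---|---|---|
| 4 | P(Z ≥ 0) = 50%, 27 of 54 | P(Z ≥ 1.25) = 10.6%, 5.7 of 54 |
| 5 | 50%, 27 of 54 | P(Z ≥ 1) = 15.9%, 8.6 of 54 |
| 8 | 50%, 27 of 54 | P(Z ≥ 0.625) = 26.6%, 14.4 of 54 |

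- Mean month-12 loss among those sampled, SD 5: 10 + 5 × 0.798 = 13.99 against 5 + 5 × (0.242/0.159) = 12.6. The contrast is about 1.4 points instead of 5.0.
- Standard error relative to 54 against 54: √(1/27 + 1/8.57) / √(2/54) = 2.04 (1.7 to 2.4 for SD 4 to 8).
- With the smaller effect in the Sample size section (3.6 ± 4.22 against 1.1 ± 3.39 kg) and an assumed 100 kg body weight: P(Z ≥ 6.4/4.22) = 6.5% and P(Z ≥ 8.9/3.39) = 0.4%, or 3.5 and 0.2 of 54. At 130 kg it is 0.7 and 0.0.

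**B. Natural reading: month-12 sample for patients without surgery**

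Hand check with the front-loaded curve (50/80/100), SD 5 and exit at the visit where the target is met. Exit by month 6 needs a month-12 loss of at least 10/0.8 = 12.5: P(Z ≥ 0.5) = 30.9% against P(Z ≥ 1.5) = 6.7%. Exit at month 3 needs 10/0.5 = 20: P(Z ≥ 2) = 2.3% against P(Z ≥ 3) = 0.1%.

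- Mean sampling month: 12 − 6(0.309) − 3(0.023) = 10.1 against 12 − 6(0.067) − 3(0.001) = 11.6.
- Loss not yet reached at sampling, combination: 0.2 × (10 × 0.309 + 5 × 0.352) + 0.3 × (10 × 0.023 + 5 × 0.054) = 1.12.
- The same for metformin: 0.2 × (5 × 0.067 + 5 × 0.130) + 0.3 × (5 × 0.001 + 5 × 0.004) = 0.20.
- Contrast at sampling: (10 − 1.12) − (5 − 0.20) = 4.1 of 5.0 points.

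Simulation over all four curves, 600,000 patients per arm:

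| Weight contrast at sampling, of 5.0 points | SD 5 | SD 4 to 8 |
|---|---|---|
| Exit at the visit where the target is met | 4.1 to 4.8 | 3.7 to 4.9 |
| Surgery one visit later | 4.9 to 5.0 | 4.6 to 5.0 |

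The second row is plausible because section 2 says "250 patients are on waiting list and preparation for this procedure". With the Sample size effect the contrast is 2.4 to 2.5 of 2.5 kg.

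**C. Sensitivity to the surgical target**

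If 10% of excess weight applied instead, with an assumed BMI of 45 and reference BMI of 25, the target would be 10 × (45 − 25)/45 = 4.44% of weight. At SD 5 the contrast under B is 2.1 to 2.4 with immediate exit (1.7 to 2.6 over an assumed BMI of 40 to 50), or 3.9 to 4.5 with a one-visit wait at BMI 45.

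**The case against.** The strongest reply is that the literal reading is not what the plan means. Item 2 provides for initial and final determinations and names month 12. Each patient is assessed for one year. The objectives compare groups before and after treatment without a responder restriction, and the data sheet has a Final column. All participants are surgical candidates, so the phrase about response most easily describes when the sample is taken, not who gives one. With the Sample size effect, a literal reading would leave almost nobody to analyse, which points to loose wording. This stands: a month-12 sample is the more natural reading, and the timing bias is then small under the item 1 target.

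It is also fair that every contrast above is for weight. The documents give nothing that carries it over to IL-6, ghrelin or glucagon. Nor is dependence on response beyond modelling in principle: exit follows weights observed at visits, and a joint model of weight and marker could use that. The plan does not specify one.

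What does not fall away is the gap itself. Items 4 and 11 foresee patients who leave without surgery, and no sentence gives them a final sample. The general schedule for biochemical variables in item 7 does not fill it, because items 2 and 9 treat these markers separately and the visit grid omits them.

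**Conclusion.** The concern holds as a gap in a stated collection rule for seven markers. If item 9 is followed to the letter, the arm comparison is confined to weight-loss responders: 50% against 11% to 27% sampled, given normal losses, the section 5 means, the 10% target and an assumed SD of 4 to 8. If month 12 is implied for the rest, the weight contrast at sampling keeps 3.7 to 4.9 of 5.0 points with immediate exit and 4.6 to 5.0 with a one-visit wait.

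A reader might infer that the trial is designed to compare responders only, or that response-dependent timing seriously biases the marker results. The documents support neither. Their other wording points to a final sample for all, the remaining timing effect on weight is small under the item 1 target, and the effect on the markers cannot be quantified. A reader might also take the gap to cover insulin. It does not: the variable table gives insulin fixed visits, although this conflicts with item 9.

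**What to change.** **Main change.** Amend item 9 to require a final ELISA sample from every randomised patient still in follow-up: at the last scheduled visit before surgery, or at month 12 if there is no surgery. Analyse all randomised patients in their assigned arms. Report by arm the number sampled and the sampling month. Sampling month should not be used as an ordinary adjustment covariate, because it is a result of response. The cost is one sentence and two descriptive lines; the plan stays at two ELISA time points per patient. The Statistical analysis paragraph is in the past tense; if sampling is already complete, the report by arm can still be made.

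**Optional.** A common month-3 assay would compare the arms at equal time. It needs up to 108 × 7 = 756 further determinations (864 with insulin), while section 11 says kit funding is still to be sought, and no passage says that serum is stored. It would also be less sensitive: the expected weight contrast at month 3 is 5.0 × 0.25 to 0.50 = 1.25 to 2.5 points, and section 7 links marker change especially to losses above 10%. It should not replace the late sample.

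**Separately.** Reconcile item 1 with section 7 on the surgical target, and item 9 with the variable table on insulin timing and assay. This review does not say which is right.
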